Study Medication: Subjects who satisfy all inclusion and exclusion criteria will be randomized to either PIO 45 mg once daily or HCQ 400 mg once daily (2 x 200 mg tablets). Randomization will occur based on the subject's (randomly assigned) unique medical record number issued by MLK or SCFHC: *odd numbers will receive HCQ; even numbers will receive PIO.* The study is open-label. The supply of PIO will be prescribed as per usual clinical practice through the outpatient pharmacies at MLK and SCFHC (or provided by the investigators if not obtainable from SCFHC because of their internal insurance coverage policies), and compliance will be determined by pill counts and referencing dispensing records from the MLK online pharmacy database (for subjects from MLK). The supply of HCQ will be purchased from a retail pharmacy specifically for the study, and compliance will be determined by pill counts assessed by the study coordinators at each follow-up visit. Subjects will be provided with a 90-day supply at the randomization visit so as to allow for potential variations in compliance and/or scheduling of the 2-month follow-up visit. Subjects must bring their remaining supply of unused medication at the every follow-up visit, and will be provided with a sufficient amount of additional HCQ at the 2-month visit to last until their final, 4-month visit (allowing again for potential variations in compliance and/or scheduling). Although all subjects should already have experience with the principles of dietary and lifestyle modifications as part of their ongoing diabetes therapy, these concepts will be reinforced at each follow-up visit.

Follow-Up Visits (Week 8, Week 16): Subjects will be seen at the CTRC in the fasting state, vital signs, weight and height will be taken, and blood will be drawn for FPG, HbA_{1c}, CBC, electrolytes, BUN, creatinine, AST, ALT, fasting insulin, and hsCRP. For subjects from MLK,

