Laboratory Measurements: All laboratory analyses except fasting insulin and hsCRP will be obtained by the respective clinic phlebotomists specified above, and conducted by the respective clinical laboratories specified above, or the CTRC. Samples for insulin and hsCRP levels will be obtained at the CTRC, banked, and will be measured in the future by the CTRC Core Lab using commercially available RIA and/or ELISA kits: Millipore HI-14K Human Insulin RIA (Millipore, Billerica, MA); MP Biomedicals 07BC-1119 ultrasensitive CRP ELISA (MP Biochemicals, Orangeburg, NY); samples for insulin and hsCRP will remain frozen until assay reagents are available for batched runs once all samples have been collected.

Statistical Analyses:

All data will be collected onto Excel spreadsheets. Non-normal data will be log-transformed, as appropriate.

Intended Primary Endpoint: *The between-group change in the HbA_{1c} level from baseline to 4 months.*

Intended Secondary Endpoints:

A) The between-group difference in the change by 4 months of: i) % of subjects achieving HbA_{1c} $< 7.5\%$, ii) FPG, iii) weight and BMI, iv) HOMA-IR and QUICKI, and v) hsCRP and leukocyte counts;

B) For each group, the within-group change by 4 months in HbA_{1c}, FPG, weight and BMI, HOMA-IR and QUICKI, hsCRP, and leukocyte counts;

C) The between-group difference in the incidence of i) all hypoglycemic events, ii) severe hypoglycemic events, and iii) all adverse events excluding hypoglycemia.

Analysis: Changes in all continuous outcome measures will be compared between groups using 2-way repeated measures ANOVA. A chi-square analysis will be used to compare the percent of subjects achieving HbA_{1c} $< 7.5\%$ between groups. Changes within groups between baseline and

4-months will be made with one-way ANOVA. We will plan to eventually conduct both an intent-to-treat (ITT) analysis (missing data imputed using last-observation carried forward) as well as a secondary analysis of only those completed subjects with mean medication compliance $\geq 90\%$.

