Data Safety Monitoring: Quarterly analyses of all accumulated safety data will be conducted, to include analyses of: a) all accumulated clinical adverse events (including the incidence of severe hypoglycemia); and b) all accumulated laboratory test abnormalities that occur after subjects have initiated their first dose of assigned study medication, and that are deemed by the investigators to represent either i) potentially clinically meaningful yet asymptomatic adverse events, or ii) clinically significant changes from baseline laboratory values that potentially represent clinically meaningful adverse events. Data collected from all enrolled subjects will be compiled by the study coordinator and reviewed and verified by the principal investigator. These cumulative data will then be presented to the CDU Data Safety Monitoring Board (DSMB, under chairperson [name] and any other members as deemed necessary by the DSMB, but excluding study co-investigator [name]) and concurrently to the IRB. The DSMB will then review the submission independently, according to their established procedures, and report their conclusions and recommendations independently to the IRB (with a copy to the PI). Usual reporting requirements for serious and non-serious adverse events to the IRB will continue to apply throughout the study, and all such instances will also be included within each quarterly DSMB report. If on any quarterly review, the cumulative safety data indicates a possible *systematic* and clinically harmful risk that a) is likely causally related to the interventional agent and cannot be otherwise explained by subjects' concurrent circumstances, and c) cannot be mitigated by minor adjustments to the manner by which the investigators conduct or monitor subjects in the study, then consideration should be given for temporary or permanent study stoppage, with or without appropriate amendments to the protocol to mitigate the risk, as deemed necessary by the DSMB and/or IRB in consultation with the PI. Permanent study stoppage shall also be reported to the study's granting agency, as appropriate.

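### Laboratory results reach the quarterly safety review through a judgement filter applied by open-label investigators, so a modest shift across one arm could be missed

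*Combined protocol and SAP*

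**What the plan says.** The Data Safety Monitoring section opens broadly: "Quarterly analyses of all accumulated safety data will be conducted, to include analyses of" two items. Item a) is "all accumulated clinical adverse events (including the incidence of severe hypoglycemia"), with no selection. Item b) is narrower. It covers laboratory abnormalities arising after the first dose "that are deemed by the investigators to represent either i) potentially clinically meaningful yet asymptomatic adverse events", or else "clinically significant changes from baseline laboratory values that potentially represent clinically meaningful adverse events". Neither branch has a grade, a numerical limit or a reference to a laboratory range.

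The coordinator compiles the package and the principal investigator verifies it. It then goes to the DSMB and, at the same time, to the IRB. Under Study Medication the protocol states: "The study is open-label".

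On timing, serious and non-serious events go to the IRB under its usual requirements throughout the study, and "all such instances will also be included within each quarterly DSMB report". The stoppage clause begins "If on any quarterly review, the cumulative safety data indicates a possible" systematic and harmful risk. Stoppage may be decided by the DSMB, the IRB or both, in consultation with the principal investigator. The DSMB is said to follow its own established procedures, which the protocol does not reproduce.

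**The concern.** The filter in item b) works one subject and one value at a time. The question put to the reviewers is about a pattern across subjects. A rise in ALT, AST or creatinine that is small in each subject but common in one arm is the kind of signal that a value-by-value judgement tends to drop and a listing by arm would show. The person judging also knows the assignment, and no predefined limit constrains the judgement.

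Sending the package to two bodies does not help here. Both receive the same compiled material, so both inherit the same selection. At stake is the sensitivity of the cumulative review for subjects still to be enrolled or still on treatment. One stated purpose of the pilot, under Sample Size Calculations, is to learn whether HCQ raises safety concerns relative to PIO, so the comparison by arm matters.

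The secondary matter is speed. The only route written for serious events to reach the DSMB is the quarterly report, and a quarter is long beside a 16-week treatment.

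**Working it through.** The plan gives no figure for safety monitoring (no event count, boundary or power), so there is nothing to reproduce. The check sets the sections side by side and then does simple arithmetic.

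**1. Where each kind of safety data goes**

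| Data | Quarterly package (Data Safety Monitoring) | Between-arm comparison (Statistical Analyses) |
|---|---|---|
| Clinical adverse events | All, item a) | Yes, secondary endpoints C |
| Leukocyte counts | If judged meaningful, item b) | Yes, secondary endpoint A: "v) hsCRP and leukocyte counts" |
| ALT, AST, creatinine, BUN, electrolytes | If judged meaningful, item b) | None named |

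The last row is the gap. These tests are drawn at weeks 8 and 16 (Follow-Up Visits), but the quarterly review is promised them only after selection, and no final analysis by arm is planned. The adverse-event comparison in endpoints C would pick up a laboratory change only if someone had first recorded it as an adverse event.

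**2. Size of the unselected data**

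- Subjects: up to 60 (Sample Size Calculations; a funding cap).
- Scheduled post-dose panels per subject: 2 (weeks 8 and 16).
- 60 × 2 = 120 scheduled panels at most. Interim visits could add a few.

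A volume of this size gives no evident reason to pre-select.

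**3. Wait to the next quarterly DSMB review**

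Assumptions: a quarter *q* of 12 weeks, or 365.25/7/4 = 13.04 weeks; reviews evenly spaced; subject start times spread uniformly over the review calendar. The wait is then uniform on (0, *q*), with maximum *q* and mean *q*/2. Treatment lasts 16 weeks.

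| Quantity | Formula | *q* = 12 | *q* = 13.04 |
|---|---|---|---|
| Maximum wait, weeks | *q* | 12 | 13.04 |
| as share of treatment | *q*/16 | 75% | 82% |
| Mean wait, weeks | *q*/2 | 6.0 | 6.5 |
| as share of treatment | *q*/32 | 38% | 41% |
| Week-8 result reviewed before that subject's week 16 | 8/*q* | 0.67 | 0.61 |
| Event at a random time on treatment reviewed before that subject finishes | 1 − *q*/32 | 0.63 | 0.59 |
| Mean reviews during one subject's treatment | 16/*q* | 1.33 | 1.23 |

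Since *q* is below 16, every subject who completes treatment has at least one review during it. Time to compile and verify the package is extra. These figures concern the DSMB route only, not reporting to the IRB.

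**The case against.** The strongest defence is that the section starts from all accumulated safety data and introduces the two items with inclusive wording, so item b) need not be exhaustive. The bar in item b) is also low, since an abnormality need only be potentially meaningful. Both points are fair, and they rule out saying that an arm-wide shift can never reach the reviewers. They do not remove the concern. For routine laboratory results item b) is the natural reading, because the qualifier would otherwise have no purpose, and a low bar applied value by value is still not a comparison by arm.

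A reader might infer four stronger things that the documents do not support:

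- *That the DSMB alone watches the cumulative data.* The IRB receives the same package concurrently and can act on stoppage.
- *That the DSMB hears of serious events only once a quarter.* This is drawn from silence. The text says such events are also in the quarterly report, and the board's own procedures are not shown. What can be said is that no expedited route is written here.
- *That investigators would read a fall in white cells on HCQ as benefit and hold it back.* The endpoint has no stated direction, the Background anticipates a fall in hsCRP only, and leukocyte counts are compared between arms at the end.
- *That a serious event typically waits for most of a treatment course.* That is the worst case for one subject. The mean wait is about 6.5 weeks, the cumulative review still protects later enrollees, and individual protection does not wait for the DSMB, since Withdrawals and usual IRB reporting operate throughout.

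Nor does the filter delete anything from the study database. The final comparisons of leukocytes, hypoglycemia and other adverse events stand. For ALT, AST and creatinine that answer fails, because no such comparison is planned.

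**Conclusion.** The point holds for the laboratory data. Item b) makes what the quarterly review sees depend on unblinded judgement without predefined limits, and the tests most exposed (ALT, AST, creatinine) have no between-arm comparison elsewhere in the plan. A modest shift across one arm could be missed; the documents do not show that it would be. No size can be put on that risk, because they give no laboratory distributions or expected effects. The remedy can be sized: at most 120 scheduled panels.

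The timing point is secondary. No expedited route to the DSMB is written, and the wait for the next quarterly review is at most about 13 weeks and about 6.5 weeks on average, assuming evenly spaced reviews and uniform start times.

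This is a cheap and worthwhile improvement to safety oversight. It changes no sample size, power or significance level, and it does not call the trial's validity into question.

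**What to change.** **Main change.** In item b) of Data Safety Monitoring, replace the selection by investigators with a complete listing: every post-dose blood count, electrolyte, BUN, creatinine, AST and ALT result, by subject, visit and assigned arm, with the baseline value, the change from it, and a flag for values outside the reference range of the laboratory that ran the test. Keep the investigator's assessment as an added column, so that the clinical reading is seen beside the data and does not decide what is shown.

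**Secondary change.** State that each serious-event report sent to the IRB is copied to the DSMB chair at the same time, and that the chair may call a review on receipt. That gives any review outside the quarterly cycle a defined trigger and convenor. The stoppage clause should then recognise a review called in this way; its criteria need not be touched.

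**Cost.** Protocol wording, a spreadsheet listing of results the study already collects, and one copied report per serious event. The downside is a longer listing for the DSMB and IRB to read. No new tests or visits are needed.
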